## 3 ACCOUNTABILITY/DEMOGRAPHICS

#### 3.1 ENROLLMENT/ACCOUNTABILITY

The number of enrolled subjects will be tabulated by site for primary and fellow eyes. Subject accountability will be summarized as a frequency distribution by scheduled visits. A frequency table by IOL will be generated, showing the number of available eyes (those in interval and outside of the interval) and the number of missing and active subjects.

### 3.2 DEMOGRAPHICS

Subject demographic data including age, sex, race, and eye color will be presented by IOL group. Age will be determined at the time of the preoperative visit and will be categorized by less than 60, 60 to 69, 70 to 79, and equal to or older than 80 years old. In addition, age will be summarized with descriptive statistics. The frequency distributions of sex, race, and iris color will also be tabulated.

## 4 POSTOPERATIVE ANALYSES – PRIMARY ENDPOINTS

There are two primary endpoints for this study, rate of bothersome visual symptoms and rate of difficulty with an activity due to the symptoms at 6-month postoperative.

The first primary endpoint is the rate of bothersome visual symptoms,

The second primary endpoint is the rate of reported difficulty with an activity due to one or more visual symptoms, determined by a

"Yes" response to the question "Is there anything you have a lot of difficulty with, or do not do, because of [visual symptom]") at 6 months postoperative.

The frequency and proportion of subjects with bothersome visual symptoms and the frequency and proportion of subjects reporting difficulty with an activity due to one or more visual symptoms will be reported along with the two-sided, 95% confidence interval at the 6-month visit.

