1. SYNOPSIS	
PROTOCOL TITLE:	Post-Approval Study of the TECNIS Symfony [®] Toric Lenses
Protocol Number:	TIOL-205-STPA
STUDY TREATMENTS:	Toric Study Lenses:
	TECNIS Symfony Toric Extended Range of Vision IOL (Symfony Toric), Model ZXT300
	TECNIS Symfony Toric Extended Range of Vision IOL (Symfony Toric), Model ZXT375
	Toric Control Lens:
	 TECNIS Symfony Toric Extended Range of Vision IOL (Symfony Toric), Model ZXT150
	Other Study Lenses (may be used for fellow eyes):
	TECNIS Symfony Toric Extended Range of Vision IOL (Symfony Toric), Model ZXT225
	 TECNIS Symfony Extended Range of Vision IOL (Symfony), Model ZXR00
STUDY OBJECTIVE:	The purpose of this post-approval study is to evaluate the rates of bothersome visual symptoms in a larger population in clinical practice for the TECNIS Symfony Toric IOLs with approximately 2.0 D or more of cylinder correction at the corneal plane (Models ZXT300 and ZXT375, higher-cylinder group), compared to the Symfony Toric IOL with approximately 1.0 D of cylinder correction at the corneal plane (Model ZXT150, lower-cylinder group), and to ensure the continued safety of the approved devices.
CLINICAL HYPOTHESIS:	The rate of bothersome visual symptom items
	for the Symfony Toric IOL higher-cylinder

group.

group will be comparable to that of the lower-cylinder

OVERALL STUDY DESIGN:	
Structure:	Prospective, multicenter, bilateral, non-randomized, open-label, comparative clinical study
Number of Sites:	Up to 50 sites in the USA
Duration:	6 months; however, any subject that undergoes a lens repositioning procedure due to IOL misalignment, or
	at 6 months, will be followed through 1 year postoperatively.
Administration:	Surgeons will perform routine small-incision, cataract surgery and use the JJSV-recommended implantation systems for lens implantation. Refractive target outcomes will be emmetropia for both eyes.
Visit Schedule:	Subjects will be bilaterally implanted; the second eye is to be implanted within approximately one month after the first-eye surgery.
	All subjects will undergo a minimum of 9 visits: Preoperative for both eyes; Operative, 1-day and 1-week visits for each eye; and 1-month and 6-month visits for both eyes together. In addition, a 1-year postoperative visit will be required for subjects who undergo a lens repositioning procedure due to IOL misalignment at any time during the study, and for subjects who report

STUDY POPULATION CHARACTERISTICS:

Condition:

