Other endpoints are individual visual symptom ratings included in the PRVSQ, rates of IOL repositioning procedures (secondary surgical intervention) due to IOL misalignment, rates of explants due to visual symptoms, distance visual acuities, mean percent reduction in absolute cylinder, mean refractive cylinder, mean refractive cylinder compared to the preoperatively-predicted cylinder, mean spherical equivalent, spherical equivalent compared to the preoperatively-predicted spherical equivalent, percent of eyes with cylinder and spherical equivalent (MRSE) within 0.50 D and within 1.00 D of the preoperatively-predicted spherical equivalent, rates of medical and/or lens findings, and rates of other adverse events. Preoperatively-predicted values will be based upon those generated from the TECNIS Symfony Toric IOL calculator.

DATA ANALYSIS:

The key time frame for analysis will be the 6-month visit. The first primary endpoint for this study will be the rate of bothersome visual symptoms,

The second primary endpoint will be the rate of those having a lot of difficulty with an activity due to halos, glare or starbursts as measured in the PRVSQ. The primary endpoint results will be compared between higher-cylinder toric IOL subjects and lower-cylinder toric control IOL subjects at the 6-month visit. The frequency, proportion and 95% Confidence Interval (CI) will be reported for higher-cylinder and lower-cylinder control subjects. This will be done for the higher-cylinder (ZXT300 and ZXT375) and lower-cylinder (ZXT150) groups.

Descriptive statistics will be used for reporting results. Visual acuity data will be reported by acuity line achieved. For questionnaire items, the frequency and proportion for each response will be reported. For refractive data, descriptive statistics will include mean, standard deviation, median, minimum and maximum and also the percent achieving absolute values within 0.50 D and 1.00 D of preoperatively-predicted values.

The frequency and proportion of primary and fellow eyes with adverse events or medical/lens findings will also be reported.

STUDY VISITS AND PROCEDURES:

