3. CLINICAL HYPOTHESIS

The rate of bothersome visual symptom items

for the

Symfony Toric IOL higher-cylinder group will be compared to the rate for the lower-cylinder group. The bothersome visual symptom items of interest are halos, glare, and starbursts.

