6. STUDY OBJECTIVES AND ENDPOINTS

The objective of this post-approval study is to evaluate the rate of bothersome visual symptoms

at 6 months for the Symfony Toric IOLs with approximately 2.0 D or more of cylinder correction at the corneal plane (Models ZXT300 and ZXT375) in a larger population in clinical practice compared to the control IOL (Symfony Toric Model ZXT150 IOL), and to ensure the continued safety of the approved devices.

Study endpoints will be evaluated at 6 months postoperatively.

6.1 **PRIMARY ENDPOINT:**

The primary co-endpoints are the rate of bothersome visual symptoms and the rate of difficulty with an activity due to the symptoms at 6 months postoperative.

The rate of difficulty with an activity due to the symptoms is determined by the percentage of subjects who respond "Yes" to the question "Is there anything you have a lot of difficulty with, or do not do, because of (visual symptom) at 6 months postoperative.

The frequency and proportion of subjects reporting one or more of these items

via PRVSQ questionnaire will be used to

determine the primary endpoint. This rate will be calculated for the higher-cylinder (ZXT300 and ZXT375) and lower-cylinder (ZXT150) groups.

6.2 OTHER ENDPOINTS:

- Other questionnaire responses, such as rates of degree of bother
- Rates of IOL repositioning procedures (secondary surgical intervention) due to IOL misalignment
- Rate of explants related to visual symptoms
- Rates of other adverse events
- Monocular uncorrected distance visual acuity
- Monocular best corrected distance visual acuity

- Mean percent reduction in absolute cylinder
- Mean refractive cylinder and mean refractive cylinder compared to preoperatively-predicted cylinder
- Mean spherical equivalent and mean spherical equivalent compared to preoperatively-predicted spherical equivalent
- Percent of eyes with absolute cylinder within 0.50 D and within 1.00 D of preoperatively-predicted cylinder
- Percent of eyes with spherical equivalent within 0.50 D and within 1.00 D of preoperatively-predicted spherical equivalent
- Rates of medical and/or lens findings

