21.4 INTERIM REPORTS

21.5 SAMPLE SIZE CALCULATIONS

With a sample size of 240 subjects and assuming a 20% rate of bothersome visual symptoms or difficulty with an activity due to visual symptoms, a two-sided 95% confidence interval will estimate the observed rate of bothersome visual symptoms to within 4.2 percentage points.

[figure not shown]
To achieve 240 higher-cylinder group subjects and 240 lower-cylinder group subjects evaluable at 6 months, assuming an initial 20% screen-fail rate and a 5% lost-to-follow-up rate, up to 634 total subjects will be enrolled.

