### APPENDIX I: TABLE LISTING

**TIME FRAME**: The 6-month postoperative visit is the key timeframe for reporting. **STATISTICS**: See text portion of the statistical analysis plan for information on inferential statistics for comparisons between IOL group

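### The stated precision of 4.2 points should be about 5.1 for a two-sided 95% interval, and no visible precision figure covers the between-group difference

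*SAP*

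**What the plan says.** **Precision.** Protocol 21.5 and SAP 7 take 240 subjects and an assumed 20% rate, and say that a two-sided 95% interval "will estimate the observed rate of bothersome visual symptoms to within 4.2 percentage points". Protocol 21.2 gives the same figure and makes clear that the 240 is per group. No second precision figure is visible.

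**The question.** Protocol section 6 sets the objective as evaluating the higher-cylinder lenses "in a larger population in clinical practice compared to the control IOL (Symfony Toric Model ZXT150 IOL"). The synopsis states: "The primary endpoint results will be compared between higher-cylinder toric IOL subjects and lower-cylinder toric control IOL subjects at the 6-month visit". Protocol section 3 says that the rate for the "Symfony Toric IOL higher-cylinder group will be compared to the rate for the lower-cylinder group". The synopsis hypothesis is that the rate in the higher-cylinder "group will be comparable to that of the lower-cylinder" group.

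**The primary analysis.** The synopsis specifies: "The frequency, proportion and 95% Confidence Interval (CI) will be reported for higher-cylinder and lower-cylinder control subjects". Protocol 21.2 and SAP 4 say that the frequencies and proportions "will be reported along with the two-sided, 95% confidence interval at the 6-month visit". Protocol 21.1 and SAP 2.1 have the two groups reported separately.

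**A pointer.** SAP Appendix I says: "See text portion of the statistical analysis plan for information on inferential statistics for comparisons between IOL group".

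**The concern.** The 4.2-point figure is the only quantitative justification given for 240 per group, and it looks too small for a 95% interval at 20%. If it is wrong, the plan promises more precision than it can deliver.

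The figure also describes one group's rate, whereas the stated question is about two groups. A difference between two independent rates is always estimated less precisely than either rate alone. A reader who takes 4.2 points as the precision of the study's answer is therefore misled twice: the one-group figure is too small, and it is not the figure for the comparison.

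Finally, if no measure or interval method for the comparison is fixed in advance, both would be chosen after the counts are known, in an open-label study.

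**Working it through.** **Inputs.** From Protocol 21.2 and 21.5 and SAP 7: n = 240 evaluable per group, p = 0.20, two-sided 95%, stated half-width 4.2 points, 20% screen failure, 5% loss to follow-up, 634 enrolled.

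**1. The plan's own precision figure.** Half-width = z × √(p(1−p)/n), with √(0.20 × 0.80 / 240) = 0.02582.
- 95%, z = 1.960: 1.960 × 0.02582 = 0.0506, or **5.06 points**. The interval is about 14.9% to 25.1%, not 15.8% to 24.2%.
- 90%, z = 1.645: 1.645 × 0.02582 = 0.0425, or 4.25 points.

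The choice of method does not explain the gap. Average 95% half-widths for 48/240 are: Wilson 5.04, Jeffreys 5.04, Agresti-Coull 5.06, Clopper-Pearson 5.25, Wald with continuity correction 5.27. None gives 4.2.

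Working backwards at 95%:
- n for 4.2 points at 20%: (1.960/0.042)² × 0.16 = 348.4, so 349 per group.
- Rate at which n = 240 gives 4.2 points: about 12.6%.

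**2. Enrolment.** 240/0.95 = 252.6, so 253 per group (506 in total). 253/0.80 = 316.25, so 317 per group (634 in total). Both totals reproduce. They start from 240, not from 4.2, so correcting the precision does not alter them.

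**3. Precision of the difference.** Half-width = z × √(2p(1−p)/n) = 1.960 × √(0.32/240) = 1.960 × 0.03651 = 0.0716, or **7.16 points**. Newcombe's interval for 48/240 v 48/240 is −7.16 to +7.16.

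Only the 20% row below uses the documents' rate. The other rates are assumptions to show the range.

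| Rate in both groups | One group, 95% | Difference, Wald 95% | Difference, Newcombe 95% |
|---|---|---|---|
| 10% | 3.80 | 5.37 | 5.47 |
| 20% | 5.06 | 7.16 | 7.16 |
| 30% | 5.80 | 8.20 | 8.16 |

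Under the Wald formula the difference is √2 = 1.41 times less precise than one rate. At 20% it is 7.16/4.2 = 1.70 times the stated figure.

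**4. Illustration (the 25% is assumed).** Suppose 60/240 (25%) in the higher-cylinder group and 48/240 (20%) in the lower. Reported separately, the Wilson intervals are 19.9% to 30.8% and 15.4% to 25.5%. The difference is 5.0 points, with a Newcombe 95% interval of −2.5 to 12.4. The two overlapping intervals do not show directly that an excess of about 12 points remains compatible with the data.

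**5. What the visible text names.** The synopsis promises a comparison and lists a frequency, proportion and interval for the two groups. The sentences in Protocol 21.2 and SAP 4 do not say whose interval is meant; separate reporting of the groups makes the per-group reading likely, but it is an inference. No visible section names a difference, a ratio or an interval method for a between-group contrast.

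**The case against.** The strongest objection concerns the comparison. A reader might infer that the plan fails to specify any between-group analysis. The documents do not support that. SAP Appendix I says that the SAP text covers inferential comparisons between groups, and there are places where it could sit: SAP numbering goes from 5.5 to 7 with no section 6 shown, a sentence in SAP 2.1 about the final report breaks off, and Protocol 21.4 has a heading without text. The Appendix I sentence could equally be a template leftover; the visible text cannot settle which. This part therefore stands only as a request for confirmation.

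It is also fair to say that the synopsis calls for descriptive statistics, and that two rates with their intervals side by side can count as a descriptive comparison. The difference can be calculated later from the reported counts, so no data are lost, and two binary endpoints at one visit leave limited room for selective analysis. The √2 factor holds for any design with two equal groups and is not a defect. Newcombe's method and the difference scale are choices, not corrections. The groups are not randomized and differ in the fellow-eye lenses permitted, so an unadjusted difference needs careful labelling.

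None of this touches the 4.2-point figure, which is stated in full in three visible places and fails on its own inputs.

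**Conclusion.** The stated precision is wrong as written. With 240 per group and a 20% rate, the two-sided 95% half-width is about 5.1 points (5.0 to 5.3 across the methods tried), roughly 20% wider than the 4.2 claimed (5.06/4.2 = 1.20). This rests only on the documents' own inputs. That 4.2 matches a 90% interval is an observation about the number; the documents do not say how it arose, and they consistently specify 95%. Nor should a reader infer that 634 is miscalculated: it follows correctly from 240 per group.

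The second part is secondary and conditional. The stated question is comparative, but the visible precision statement covers one group's rate. The corresponding figure for the difference is about 7.2 points, assuming 20% in both groups, 240 evaluable in each, and independent subjects. Whether a between-group interval is already planned cannot be decided from the visible text.

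**What to change.** 1. In Protocol 21.2, Protocol 21.5 and SAP 7, change 4.2 to about 5.1 percentage points. Enrolment stays as it is.
2. In Protocol 21.5 and SAP 7, add: *If the true rate is 20% in both groups and 240 are evaluable in each, the half-width of the two-sided 95% interval for the difference in rates is about 7.2 percentage points.*
3. Confirm which SAP section Appendix I refers to and put its number in the pointer. If there is no such text, add to SAP 4: *For each primary endpoint, the 6-month rate in the higher-cylinder group minus that in the lower-cylinder group will be presented descriptively with a two-sided 95% interval by a named method (for example Newcombe). The estimate is unadjusted and the groups were not randomized.*

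The cost is one figure corrected in three places, one added sentence on precision in each document, a section number in the pointer and, if item 3 applies, one more SAP sentence and one extra line per primary table. No new data or subjects are needed. The downsides are a less favourable stated precision and the chance that an unadjusted difference is over-read, which the labelling is meant to limit.

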# 5 POSTOPERATIVE ANALYSIS: OTHER ENDPOINTS

## 5.1 VISUAL ACUITY ENDPOINTS

Visual acuity will be reported by high and low cylinder group. The frequency and proportion of eyes achieving each line of visual acuity will be reported.

## 5.2 MANIFEST REFRACTION

Descriptive statistics of mean percent reduction in cylinder, refractive cylinder, cylinder vs preoperatively-predicted cylinder, spherical equivalent and spherical equivalent vs preoperatively-predicted spherical equivalent will be reported by IOL group. The frequency and proportion of eyes within 0.50 D and within 1.00 D of the preoperatively-predicted values will be reported for refractive cylinder and spherical equivalent. Percent reduction in cylinder will be calculated for each eye using the following formula:

100\*((Postop Ref. Cyl. - Preop K. Cyl.)/(Target Ref. Cyl. - Preop K. Cyl. )) Key: Ref. Cyl.=absolute refractive cylinder; K. Cyl.=keratometric cylinder;

Refractive data will be referred to the corneal plane prior to determining percent reduction in cylinder.

## 5.3 OTHER QUESTIONNAIRE ENDPOINTS

The frequency and proportion with each response will be reported for the individual visual symptom items on the questionnaire and will be reported by high and low cylinder group for bilateral subjects.

## 5.4 SAFETY ENDPOINTS/MEDICAL/LENS FINDINGS

The frequency and proportion of medical and lens findings will be reported for primary and fellow eyes of toric subjects. The frequency and proportion of adverse events at any time postoperative will also be reported.

A listing of serious adverse event or device-related events will also be provided for all subjects. Rates of IOL repositioning procedures (secondary surgical intervention) due to IOL misalignments, rates of explants due to visual symptoms will also be reported.

#### 5.5 NON-DIRECTED OCULAR/VISUAL SYMPTOMS

Rates of postoperative non-directed ocular/visual symtpoms will be tabulated with the frequency and proportion of eyes with these events reported over time by IOL group.

## 7 SAMPLE SIZE CALCULATIONS

With a sample size of 240 subjects and assuming a 20% rate of bothersome visual symptoms or difficulty with an activity due to visual symptoms, a two-sided 95% confidence interval will estimate the observed rate of bothersome visual symptoms to within 4.2 percentage points.

To achieve 240 higher-cylinder group subjects and 240 lower-cylinder group subjects evaluable at 6 months, assuming an initial 20% screen-fail rate and a 5% lost-to-follow-up rate, up to 634 total subjects will be enrolled.

### APPENDIX I: TABLE LISTING

**TIME FRAME**: The 6-month postoperative visit is the key timeframe for reporting. **STATISTICS**: See text portion of the statistical analysis plan for information on inferential statistics for comparisons between IOL group

